4.6.4 Diarrhea

In addition to oral cephalosporin prophylaxis, other guidelines for patients with dose-limiting diarrhea include consideration of the possibility of cholinergic syndrome if diarrhea occurs within hours of the irinotecan infusion. Patients with early diarrhea may benefit from pretreatment with atropine (0.01 mg/kg IV; max dose 0.4 mg), as well as prolonging the irinotecan infusion to 90 minutes. Additional strategies for treating patients with therapy-associated diarrhea are given in section 5.5.

Patients who continue to have dose-limiting diarrhea despite cephalosporin prophylaxis and other measures above should have the dose of irinotecan reduced by 25% to 37.5 mg/m²/dose. These patients should continue to receive the above supportive therapies with subsequent cycles.

Patients with recurrent dose-limiting diarrhea despite supportive measures and irinotecan dose reduction should have the dose of irinotecan reduced by another 25% of the initial starting dose to 25 mg/m²/dose.

If diarrhea remains dose-limiting despite two irinotecan dose reductions, MLN8237 should be reduced by one dose level. Patients already receiving dose level -1B or an absolute dose of MLN8237 of 10 mg and who require dose reduction will be removed from protocol therapy. Patients with recurrent dose-limiting diarrhea despite these dose reductions should be removed from protocol therapy.

4.6.5 Mood alterations

Patients who develop dose-limiting mood alteration while receiving MLN8237 should have the remainder of the MLN8237 for that cycle held. These patients should have their dose of MLN8237 reduced one dose level with their next cycle of therapy. Patients already receiving dose level -1B or an absolute dose of MLN8237 of 10 mg and who require dose reduction will be removed from protocol therapy.

Patients with recurrent dose-limiting mood alteration despite initial MLN8237 dose reduction should have their dose of MLN8237 reduced by another dose level. Patients already receiving dose level -1B or an absolute dose of MLN8237 of 10 mg and who require dose reduction will be removed from protocol therapy.

Patients with recurrent dose-limiting mood alteration despite these dose reductions will be removed from protocol therapy.

4.6.6 Other toxicities

Patients who develop other dose-limiting non-hematologic toxicities (per section 4.4) should have their dose of MLN8237 reduced by one dose level. Patients already receiving dose level -1B or an absolute dose of MLN8237 of 10 mg and who require dose reduction will be removed from protocol therapy.

Patients with recurrent dose-limiting toxicity despite initial MLN8237 dose reduction should have their dose of MLN8237 reduced by another dose level. Patients already receiving dose level -1B or an absolute dose of MLN8237 of 10 mg and who require dose reduction will be removed from protocol therapy.

Patients with recurrent dose-limiting toxicity despite these dose reductions will be removed from protocol therapy.

4.7 Concomitant Therapy

- 4.7.1 No other cancer chemotherapy or immunomodulating agents will be used.
- 4.7.2 Palliative radiotherapy is not allowed on study.
- 4.7.3 Appropriate antibiotics, blood products, anti-emetics, fluids, electrolytes and general supportive care are to be used as necessary (see Section 5.0).
- 4.7.4 Patients may not receive cyclosporine, digoxin, tacrolimus, or sirolimus while on study.
- 4.7.5 Use of as-needed benzodiazepines is allowed, though discouraged. Caution should be taken with concomitant use of as-needed benzodiazepines with MLN8237. Such patients may be at increased risk for mood alteration and sedation due to combined GABA-ergic effects of both drugs.

Use of scheduled benzodiazepines (defined as at least once daily on a chronic scheduled basis) is not allowed.

- 4.7.6 Systemic antacids (both H2 receptor antagonists and proton pump inhibitors) may decrease MLN8237 exposure and should be avoided during MLN8237 treatment. Locally-acting antacids should not be taken simultaneously with MLN8237 but antacids can be given up to 2 hours prior or 2 hours following MLN8237 administration.
- 4.7.7 Enzyme-inducing anticonvulsants (phenobarbital, phenytoin, carbamazepine) must not be used as these may interfere with irinotecan metabolism. Non-enzyme inducing anticonvulsants (Keppra, etc.) can be used after discussion with study chair. The use of high dose dexamethasone and the use of aprepitant as antiemetics is not recommended due to effects on irinotecan metabolism

5.0 SUPPORTIVE CARE

5.1 Prophylaxis for Pneumocystis Pneumonia

All patients should receive PCP prophylaxis according to institutional guidelines.

5.2 Use of Myeloid Growth Factors

Myeloid growth factor support is now required for all patients, as above.

5.3 Antiemetics

This combination may be emetogenic. Patients should receive antiemetic(s) starting a minimum of 30 minutes prior to the first dose of oral chemotherapy on days 1-7. Use of benzodiazepines as a scheduled antiemetic is prohibited. Use of benzodiazepines as an as needed antiemetic is discouraged. The use of high dose dexamethasone and the use of aprepitant as antiemetics is not recommended due to effects on irinotecan metabolism.

5.4 Treatment of Irinotecan-Associated Diarrhea

Irinotecan-associated diarrhea can be profuse and can occur either early (minutes to hours) or late (days) in the treatment schedule. Early diarrhea results from cholinergic stimulation, while late diarrhea relates to bacterial processing of irinotecan metabolites.

Early diarrhea: Patients who have the onset of diarrhea during the irinotecan infusion or in the hours following the completion of an irinotecan infusion should receive atropine (suggested dose 0.01 mg/kg IV, maximum dose 0.4 mg). Early onset diarrhea is usually accompanied by cholinergic manifestations (diaphoresis and abdominal cramping). Since irinotecan is being administered on a prolonged schedule (daily x 5), it may be difficult to distinguish early versus late diarrhea. If a patient with presumed early diarrhea does not improve with administration of atropine, they should be instructed to begin treatment for late diarrhea. Patients with suspected early diarrhea should also have the duration of subsequent Irinotecan infusions prolonged to 90 minutes.

Late diarrhea (more than 24 hours after irinotecan administration): Patients will be given loperamide for late diarrhea based on body weight according to the following chart. Each family will be instructed to have loperamide available and begin treatment at the first episode of poorly formed or loose stools or the earliest onset of bowel movements more frequent than normally expected for the patient. Families should be given the handout in Appendix V. Patients will also be instructed to contact their physician if any diarrhea occurs.

Maximum dose of loperamide per day: < 6 years: 4mg/day; 6-11 years: 6mg/day; >11 years: 16 mg/day, using the non silicone-containing product.	
Weight: > 43 kg:	4 teaspoons or 2 caplets (4 mg) after the first loose bowel movement, followed by 2 teaspoons or 1 caplet (2mg) every 2 hours. During the night the patient may take, 2 caplets (4mg) every 4 hours rather than 1 caplet (2mg) every 2 hours.
Weight: 30kg – 43kg:	2 teaspoons or 1 caplet (2mg) after the first loose bowel movement followed by 1 teaspoon or one-half caplet (1 mg) every 2 hours. During the night the patient may take, 1 caplet (2 mg) every 4 hours rather than one-half caplet every 2 hours.
Weight: 20kg – < 30kg:	2 teaspoons or 1 caplet (2mg) after the first loose bowel movement followed by 1 teaspoon or one-half caplet (1mg) every 3 hours. During the night, the patient may take 1 caplet (2mg) every 4 hours rather than one-half caplet every 3 hours.
Weight: 13kg - < 20kg:	1 teaspoon (1mg) after the first loose bowel movement followed by 1 teaspoon (1mg) every 3 hours. During the night, the patient may take 1 teaspoon (1 mg) every 4 hours rather than every 3 hours.
Weight: < 13kg:	Half teaspoon (0.5mg) after the first loose bowel movement followed by half teaspoon every 3 hours. During the night, the patient may take half teaspoon (0.5mg) every 4 hours rather than every 3 hours.

[figure not shown]
If there is failure of loperamide to control severe diarrhea after 24 hours of use, patients should be considered for treatment with **octreotide** (Sandostatin™) at the dose of **10 micrograms/kg/dose** subcutaneously every 12 hours x 3 days.

Patients receiving prolonged exposure to antibiotics (i.e., cefixime) who develop diarrhea should have stool samples evaluated for *C difficile* toxin, as this is a potentially treatable cause of diarrhea. If patients have fever with diarrhea, or bloody diarrhea, evaluation of stools for bacterial culture should also be performed.

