APPENDIX V: PATIENT INSTRUCTIONS FOR TREATING DIARRHEA

Be aware of your/your child's bowel movements. At the first sign they become softer than usual or if your child has any increase in the number of bowel movements over what is normal for him/her, then you/your child should begin taking loperamide (Imodium). **If he/she does not start taking the loperamide right away, the diarrhea may become severe and last several days or require hospitalization.**

Please follow these directions carefully, using dosing guidelines below:

Take _____ loperamide at the first sign of diarrhea.

Continue taking _____ loperamide every _____ hours until your normal pattern of bowel movements returns. Repeat the same doses and frequency if the diarrhea returns.

Do not give more than _____ of loperamide in a 24 hour period.

Please call your doctor if you have any questions about taking loperamide, if your child's diarrhea is not under control after two days, or if he/she is feeling extremely weak, lightheaded, or dizzy.

Make an extra effort to give your child lots of fluids (several glasses of pedialyte, fruit juices, soda, soup, etc.) while your child is participating in this study.

Side effects may include tiredness, drowsiness, or dizziness. If your child experiences these side effects, or if your child is urinating less frequently than usual, please contact your child's physician.

Do not give your child any laxatives without consulting with his/her physician.

Loperamide dosing guidelines:

Loperamide is usually supplied in the following forms: 1 teaspoon = 1mg; 1 caplet = 2mg

Maximum dose of loperamide per day: < 6 years: 4 mg/day; 6-11 years: 6 mg/day; >11 years: 16 mg/day, using the non silicone-containing product.

Weight: > 43 kg: 4 teaspoons or 2 caplets (4 mg) after the first loose bowel movement, followed by 2 teaspoons or 1 caplet (2mg) every 2 hours. During the night the patient may take, 2 caplets (4mg) every 4 hours rather than 1 caplet (2mg) every 2 hours.

Weight: 30kg – 43kg: 2 teaspoons or 1 caplet (2mg) after the first loose bowel movement followed by 1 teaspoon or one-half caplet (1 mg) every 2 hours. During the night the patient may take, 1 caplet (2 mg) every 4 hours rather than one-half caplet every 2 hours.

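### The Appendix V family handout sets a two-day call point that contradicts Section 5.4, and its loperamide continue and repeat lines are not made subject to the printed daily maximum

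*Combined protocol and SAP*

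**What the plan says.** Section 5.4 covers late irinotecan diarrhea. It gives an age-based ceiling, "Maximum dose of loperamide per day: < 6 years: 4mg/day; 6-11 years: 6mg/day; >11 years: 16 mg/day", followed by a chart by weight. Above 43 kg the first dose is 4 mg, "followed by 2 teaspoons or 1 caplet (2mg) every 2 hours". At 13 to <20 kg the chart reads "1 teaspoon (1mg) after the first loose bowel movement followed by 1 teaspoon (1mg) every 3 hours". Each band has an optional night regimen at 4-hour spacing; at 20 to <30 kg it is "During the night, the patient may take 1 caplet (2mg) every 4 hours rather than one-half caplet every 3 hours".

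On contact and escalation, Section 5.4 says "Patients will also be instructed to contact their physician if any diarrhea occurs". It then addresses clinicians: "If there is failure of loperamide to control severe diarrhea after 24 hours of use, patients should be considered for treatment with" octreotide.

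The document families take home is the handout: "Families should be given the handout in Appendix V". Appendix V reprints the same ceilings and chart. Its instruction lines contain blanks for the site to complete: an amount of "loperamide at the first sign of diarrhea", a repeat amount, an interval and a 24-hour limit. Families are told to keep dosing at the interval until stools are back to normal, and to use the same doses and frequency again if diarrhea comes back. The next line forbids exceeding the filled-in 24-hour limit. The handout asks for a call if diarrhea is still uncontrolled at two days. It also asks for contact over questions about loperamide, extreme weakness, lightheadedness or dizziness, tiredness or drowsiness, and reduced urination.

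**The concern.** There are two separate problems.

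1. **When to call.** The protocol body has families contact the physician for any diarrhea. For uncontrolled diarrhea, the sheet they keep at home names two days. A family relying on the sheet could wait when the protocol wants contact at once.

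2. **Schedule against ceiling.** If diarrhea lasts through the day, a child dosed at the printed interval passes the printed maximum in most weight and age groups. A family that keeps to the interval goes over the limit. A family that keeps to the limit stops part-way through the day, and nothing on the sheet links that moment to a call.

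Diarrhea lasting a full day is foreseeable. Section 5.4 describes it as potentially profuse, and the handout warns that it can last several days if loperamide is not started promptly. Section 2.11 reports grade 3 diarrhea in three of six patients at dose level 1, before cephalosporin prophylaxis became mandatory. Section 3.2.1 admits patients from 12 months of age, so the 4 and 6 mg ceilings apply to children who can enroll.

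**Working it through.** **Inputs** (Section 5.4 chart, repeated in Appendix V). Ceilings: 4 mg under 6 years, 6 mg at 6–11 years, 16 mg over 11 years.

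| Weight | First dose | Day repeat | Night option |
|---|---|---|---|
| >43 kg | 4 mg | 2 mg every 2 h | 4 mg every 4 h |
| 30–43 kg | 2 mg | 1 mg every 2 h | 2 mg every 4 h |
| 20 to <30 kg | 2 mg | 1 mg every 3 h | 2 mg every 4 h |
| 13 to <20 kg | 1 mg | 1 mg every 3 h | 1 mg every 4 h |
| <13 kg | 0.5 mg | 0.5 mg every 3 h | 0.5 mg every 4 h |

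**Step 1: first 24 hours at the day interval.** Total = first dose + repeat dose × number of repeats before hour 24 (11 repeats at 2 h, 7 at 3 h).

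- >43 kg: 4 + 11×2 = 26 mg
- 30–43 kg: 2 + 11×1 = 13 mg
- 20 to <30 kg: 2 + 7×1 = 9 mg
- 13 to <20 kg: 1 + 7×1 = 8 mg
- <13 kg: 0.5 + 7×0.5 = 4 mg

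**Step 2: with the night option.** The plan does not define the night, so I varied onset over 24 hours in 15-minute steps and night length from 6 to 10 hours. A dose due in the night moves to 4 hours after the previous one, and takes the night amount if it still falls in the night. Totals are 22–26, 11–13, 9–11, 7–8 and 3.5–4 mg. The low end for >43 kg comes from onset at night: 4 mg at hour 0, then 2 mg at hours 4, 6, …, 20 (nine doses), next dose at hour 24, so 4 + 9×2 = 22 mg.

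Other readings of the night rule shift the ranges slightly. If a deferred dose always takes the night amount, the top three bands give 24–26, 12–13 and 10–11 mg. If the larger dose is taken at bedtime, their upper ends reach 28, 14 and 12 mg. The conclusion uses the lowest figures. At 20 to <30 kg the night option raises the hourly rate: 2/4 = 0.50 mg/h against 1/3 = 0.33 mg/h.

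**Step 3: compare with the ceilings.** The lowest totals from 13 kg up are 22, 11, 9 and 7 mg. All exceed both 6 and 4 mg. Only >43 kg exceeds 16 mg. Below 13 kg the total is at most 4 mg, so no ceiling is passed.

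**Step 4: hour at which the ceiling is reached at the day interval.** Hour = interval × (ceiling − first dose) / repeat dose.

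| Weight and age | Calculation | Hour |
|---|---|---|
| >43 kg, over 11 y | 2×(16−4)/2 | 12 |
| >43 kg, 6–11 y | 2×(6−4)/2 | 2 |
| 30–43 kg, 6–11 y | 2×(6−2)/1 | 8 |
| 30–43 kg, under 6 y | 2×(4−2)/1 | 4 |
| 20 to <30 kg, 6–11 y | 3×(6−2)/1 | 12 |
| 20 to <30 kg, under 6 y | 3×(4−2)/1 | 6 |
| 13 to <20 kg, 6–11 y | 3×(6−1)/1 | 15 |
| 13 to <20 kg, under 6 y | 3×(4−1)/1 | 9 |

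**Step 5: sensitivity, waking hours only.** With no night doses, counting doses before the end of the waking period:

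- 14 hours: 4+6×2 = 16; 2+6 = 8; 2+4 = 6; 1+4 = 5; 0.5+4×0.5 = 2.5 mg
- 16 hours: 4+7×2 = 18; 2+7 = 9; 2+5 = 7; 1+5 = 6; 0.5+5×0.5 = 3 mg

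At 14 hours, >43 kg over 11 years and 20 to <30 kg at 6–11 years only equal the ceiling. At 6–11 years, 13 to <20 kg stays under it at 14 hours and equals it at 16. At either length, 30–43 kg at 6–11 years (8–9 against 6 mg) still exceeds. So, under 6 years, do 20 to <30 kg (6–7 against 4 mg) and 13 to <20 kg (5–6 against 4 mg).

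**Step 6: call points side by side.** Section 5.4 contact rule: any diarrhea. Section 5.4 octreotide point: severe diarrhea after 24 hours of loperamide. Appendix V call line: uncontrolled diarrhea after two days, hour 48 if counted from the first loperamide dose. The first and third conflict directly.

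**The case against.** The strongest reply is that a maximum is a ceiling by its nature. Both texts place it above the chart, and the handout's 24-hour stop line directly follows the continue and repeat lines. A clinician fills in the dose, interval and limit for each child and can reconcile age with weight then. This stands. A reader might infer that the handout orders an overdose, or that the plan leaves open whether interval or maximum governs. The documents do not support either reading: the maximum governs on a plain reading. What remains is that the open-ended continue and repeat lines do not refer to it.

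Second, the family is not without help. Section 5.4 calls for contact at any diarrhea, and the handout invites questions and lists symptom triggers that carry no two-day wait. So it would be wrong to infer that families have nowhere to turn for 48 hours. But none of those triggers is tied to reaching the limit, and the two-day line still contradicts the protocol body.

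Third, the octreotide point is a treatment threshold for clinicians and for severe diarrhea only. It is not a family call rule. The two-day line is later than it, which is worth noting, but the actual contradiction is with the any-diarrhea rule.

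Fourth, the totals assume dosing through a full day. With waking-hours dosing some groups only equal or stay under the maximum, as shown above. The night regimen is printed, however, and three groups exceed without it.

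**Conclusion.** The point holds as two drafting faults in a home-dosing sheet for children. The two-day call line contradicts Section 5.4; that finding is textual and needs no dosing assumption. The continue and repeat lines also cannot be followed within the maximum through a full day of persistent diarrhea. This applies to every band from 13 kg up at age 11 or under, and above 43 kg over age 11. It assumes diarrhea persists and every scheduled dose is taken. With 14–16 waking hours and no night doses it still holds for 30–43 kg at 6–11 years, and for 20 to <30 kg and 13 to <20 kg under 6 years.

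I rate it a minor patient-safety issue. The documents do not quantify harm from passing these limits or from stopping early. A reader might infer some consequence for dose-limiting toxicity rates, sample size or the response analysis; nothing in the documents supports that, and none is claimed.

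**What to change.** In Appendix V:

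- Replace the two-day call line with the Section 5.4 rule that families contact the physician for any diarrhea.
- Make the continue and repeat lines read *up to the 24-hour maximum*.
- Add: *if the maximum is reached and diarrhea continues, stop loperamide and call at once*.

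In Section 5.4, add *up to the daily maximum* to the dosing chart so that the two texts agree.

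The cost is a wording change and a reissued handout. There is no statistical cost.

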6.0 DRUG INFORMATION

6.1 MLN8237(MLN8237-004) NSC # 747888

Structure and molecular weight: MLN8237 chemical name is sodium 4-{{9-chloro-7-(2-fluoro-6-methoxyphenyl)-5H-pyrimido[5,4-d][2]benzazepin-2-yl}amino}-2-methoxybenzoate. It is a reversible and selective small molecule inhibitor of the enzyme Aurora A kinase. The structure of MLN 8237-004 is shown in the diagram below:

Pharmacology: Aurora A kinase plays a role in the regulation of chromosomal segregation during mitosis. Evidence to support that Aurora A kinase is a target for the treatment of malignancies comes from several observations. Aurora A kinase gene is amplified and/or overexpressed in many tumors. Over-expression of Aurora A kinase results in the transformation of normal cells, supporting the hypothesis that Aurora A is an oncogene. Published reports have demonstrated that in cultured tumor cells reduction of Aurora A protein content results in mitotic spindle defects, mitotic delay, and apoptosis. Inhibition of Aurora A kinase has the potential to have a role in the progression of malignancies and MLN8237 has demonstrated activity against a broad range of *in vitro* and *in vivo* preclinical tumor models.

The pharmacokinetic properties of MLN8237 were characterized in animal models and *in vitro* studies. Based on these preclinical evaluations, MLN8237 is expected to have low systemic clearance, a moderate volume of distribution at steady state, high plasma protein binding, and good oral bioavailability in humans. Due to potential for alteration of absorption by agents that modify gastric pH, proton pump inhibitors and antacids may influence the drug absorption. MLN8237 is metabolized by both glucuronidation and oxidation pathways. It is not a mechanism-based inhibitor of cytochrome P450 (CYP) 3A4/5M and is unlikely to inhibit the five major CYP enzymes, 1A2, 2C9, 2C19, 2D6, and 3A4/5, when administered at the projected human efficacious dose. Therefore, it is unlikely that MLN8237 will cause drug-drug interactions (DDIs) via inhibition of CYP-mediated metabolism. MLN8237 is a P-glycoprotein (P-gp) inhibitor. Potential DDIs may occur when MLN8237 is co-administered with a P-gp substrate. Urinary excretion of MLN8237 was negligible in the rat and chimpanzee (<1% of the dose).

Preliminary pharmacokinetic analysis of human studies showed that in the 5-150 mg once daily dose range, there is a dose-dependent increase in the area under the plasma concentration versus time curve from zero to 24 hours (AUC_{0-24hr}) and the maximum plasma concentration (C_{max}). Peak drug concentrations were generally achieved by 1 to 4 hours. The terminal half-life (t_{1/2}) was between 30 and 40 hours for doses of 5 to 80 mg and was somewhat shorter (between 10 and 30 hours) at the higher doses of 110 and 150 mg. Comparison between 7-day and 14-day administration suggested that steady-state was achieved following 7 days of dosing with lack of additional accumulation beyond Day 7. Preliminary results from pharmacokinetics studies of once and twice daily drug administration showed moderate rate of absorption with a median T_{max} of 2 hours (range 1 to 6 hours) and an overall mean half-life of about 18 hours. Twice daily dosing reduces the peak-to-trough ratio compared to once daily administration and is associated with decreased incidence of somnolence.

Toxicities: Information on MLN8237 toxicity is based on the Investigator's Brochure (Edition 9).

Inhibition of Aurora A kinase is expected to be toxic to proliferating tissues because of the role that this enzyme plays in mitosis. In preclinical experiments in rats and dogs, MLN8237 caused reversible myelosuppression and reversible injury to the gastrointestinal epithelium.

Some of the adverse events that have been observed with MLN8237 include the following: Reversible myelosuppression including leukopenia, neutropenia, febrile neutropenia, lymphopenia; thrombocytopenia; anemia; gastrointestinal toxicity including stomatitis/mucositis, oral pain, nausea, vomiting, anorexia, abdominal pain, heartburn, diarrhea, and dehydration; somnolence, confusion and disorientation and associated memory loss and gait disturbances; dependency; withdrawal symptoms; mood alteration; palmar-plantar erythrodysesthesia; abnormal liver function tests (including AST, ALT, bilirubin, ALP, and GGT); alopecia; fatigue; infection; sepsis; and fever.

MLN8237 is structurally related to benzodiazepines and has activity against the GABA α 1 receptor. Therefore there is a theoretical risk that MLN8237 could cause dependency and withdrawal symptoms. Mood changes, such as euphoria or depression, are possible. When stopping the drug, withdrawal symptoms could include: anxiety, restlessness, difficulty sleeping, tremors, rapid heart-beat, nausea and vomiting.

The use of benzodiazepines or alcohol should be limited or avoided and subjects should be instructed to avoid potentially hazardous activities that require full alertness and coordination. Concomitant use of opiates should be done with caution. Flumazenil, the selective benzodiazepine receptor antagonist, may be used as an adjunct to, but not as a substitute, for the management of life threatening sedation associated with MLN8237. In studies in adult patients, the central nervous system adverse effect of somnolence appeared to be related to peak concentrations of MLN8237 and was alleviated when dosing was changed from once to twice daily dosing.

This list of potential adverse events is most likely not comprehensive; it is possible that the drug will have other toxicities that have not been observed or predicted from its evaluation in animals or humans to date.

The frequency provided in the following table is approximate:

Adverse Events with Possible Relationship to MLN8237

Likely (>20%)	Less Likely (<= 20%)	Rare but Serious (<3%)

• Anemia• Diarrhea• Mucositis Oral• Nausea• Vomiting• Fatigue• Lymphocyte count decreased• Neutrophil count decreased• Platelet count decreased• White blood cell decreased• Anorexia• Alopecia	
• Febrile Neutropenia• Abdominal Pain/Dyspepsia• Constipation• Oral pain• Edema Limbs• Fever• Infection (including sepsis)• Alanine aminotransferase increased• Alkaline phosphatase increased• Aspartate aminotransferase increased• Blood bilirubin	
• Palmar-plantar erythrodysesthesia syndrome• Dermatitis, bullous

	
 • increased • Blood GGT increased • Creatinine increased • Dehydration • Dizziness • Headache • Cough • Dyspnea • Weakness • Rash • Sedation • Gait disturbance • Mood change and confusion • Somnolence 	
--	---	--

Also reported on MLN8237 trials but with the relationship to MLN8237 still undetermined:

BLOOD AND LYMPHATIC SYSTEM DISORDERS: Bone marrow hypocellular

CARDIAC DISORDERS - Left ventricular systolic dysfunction; Restrictive cardiomyopathy; Arrhythmia

EAR AND LABYRINTH DISORDERS - Hearing impaired; Tinnitus

EYE DISORDERS – Keratitis; Blurred Vision

GASTROINTESTINAL DISORDERS - Anal mucositis; Ascites; Colitis; Dry mouth; Dysphagia; Enterocolitis; Flatulence; Hemorrhoids; Gastrointestinal disorders, other (hepatic veno-occlusive disease)

GENERAL DISORDERS AND ADMINISTRATION SITE CONDITIONS – Chills; General disorders and administration site conditions – Other (systemic inflammatory response syndrome); General disorders and administration site conditions – Other (increased sweating); Multiorgan failure

INJURY, POISONING OR PROCEDURAL COMPLICATION - Bruising

INVESTIGATIONS - Ejection fraction decreased; Investigations - Other (pancytopenia); Weight loss

METABOLISM AND NUTRITION DISORDERS - Hypokalemia; Hyponatremia

Hyperglycemia, Hyperkalemia, Hypocalcemia, Hypomagnesemia, Hypoalbuminemia, Hypercalcemia, Hypoglycemia, Hypophosphatemia, Hypoglycemia, Blood lactate dehydrogenase increased , Metabolism and nutrition disorders – Other (failure to thrive)

MUSCULOSKELETAL AND CONNECTIVE TISSUE DISORDERS - Musculoskeletal and connective tissue disorders – Other (rhabdomyolysis); Musculoskeletal and connective tissue disorders – Other (muscle spasm); Pain in extremity, chest or back.

NERVOUS SYSTEM DISORDERS - Ataxia; Depressed level of consciousness; Dysgeusia; Memory impairment; Paresthesia; Nervous system disorders - Other (bradyphrenia); Syncope

PSYCHIATRIC DISORDERS - Confusion; Insomnia

RENAL AND URINARY DISORDERS - Acute kidney injury; Urinary incontinence

RESPIRATORY, THORACIC AND MEDIASTINAL DISORDERS - Bronchopulmonary hemorrhage; Epistaxis; Pharyngolaryngeal pain; Pleural effusion; Voice alteration

SKIN AND SUBCUTANEOUS TISSUE DISORDERS – Pruritis; Dry skin

VASCULAR DISORDERS – Hypertension; Hypotension; Thromboembolic event

Note: The MLN8237 oral solution contains propylene glycol. Ingestion of large amounts of propylene glycol can increase the risk of lactic acidosis.

Note: MLN8237 in combination with other agents could cause an exacerbation of any adverse event currently known to be caused by the other agent, or the combination may result in events never previously associated with either agent.

Formulation and Stability: MLN8237 is available as two different formulations.

The phase 1 and 2 portions of the study utilize a 10 mg enteric coated tablet. In addition to the active drug, the tablets also contain sodium bicarbonate, sodium lauryl sulfate, povidone, microcrystalline cellulose, croscarmellose sodium, and sodium stearyl fumarate. The tablets are packaged in high-density polyethylene (HDPE) bottles with a child resistant cap. Each bottle contains 10 tablets. Tablets should remain in the provided bottle until dispensing. The exact number of tablets per cycle can be counted and dispensed in prescription HDPE bottles. The tablets are stored at controlled room temperature of 20°-25°C (68°-77°F) with excursions permitted from 15°-30°C (59°-86°F).

The oral solution cohort utilizes a 5 mg/mL oral solution. In addition to the active drug, the solution also contains sodium bicarbonate, polyethylene glycol 400, propylene glycol, glycerol, acesulfame potassium, bubble gum flavor, and purified water. The solution is provided in 60 mL amber polyethylene terephthalate bottles with a child resistant cap. The solution should remain in the provided bottle until ready for dispensing in the clinic or at home. The investigational pharmacist may draw up a patient's dose on the day a patient receives therapy at the study center, but should not draw-up the full 7-day course of therapy into prefilled syringes and dispense that supply to the patient. Instead, parents/guardians will be instructed to draw up each dose at home prior to administration. The bottles are to be stored at controlled room temperature of 20°-25°C (68°-77°F) with excursions permitted from 15°-30°C (59°-86°F). Patients are to start each cycle of therapy with a new supply of bottles, rather than using any remaining solution from previous cycles.

Guidelines for Administration: See also Treatment and Dose Modification in Section 4.0.

MLN8237 is a cytotoxic anticancer drug and should be handled according to published guidelines for handling cytotoxic drugs. Tablets should not be crushed or manipulated in any way.

The oral solution formulation of the drug must be given on an empty stomach, at least one hour before and two hours after food or drink except water.

The tablet must be swallowed whole, but may be given with or without food.

Systemic antacids (both H2 receptor antagonists and proton pump inhibitors) may decrease MLN8237 exposure and should be avoided during MLN8237 treatment. Locally-acting antacids should not be taken simultaneously with MLN8237 but antacids can be given up to 2 hours prior or 2 hours following MLN8237 administration.

Antiemetics may be administered as needed; however, the use of benzodiazepines for the prophylaxis or treatment of nausea or vomiting is discouraged because of the potential benzodiazepine-like effects of MLN8237.

In case of contact with the powder or solution (e.g., from a broken tablet), skin should be washed immediately with soap and copious amounts of water for at least 15 minutes. In case of contact with the eyes, copious amounts of water should be used to flush the eyes for at least 15 minutes and patients should be instructed to notify medical personnel.

Drug Supply and Accountability: MLN8237 will be supplied by Millennium. MLN8237 will be shipped to treating directly from Millennium to treating NANT institutions. Instructions and forms for ordering MLN8237 from Millennium are posted to the NANT website.

Accountability for MLN8237 at the trial site is the responsibility of the investigator. The investigator will ensure that the study drug is used only in accordance with this protocol. Where allowed, the investigator may choose to assign some of the drug accountability responsibilities to a pharmacist or other appropriate individual. Drug accountability records indicating the drug's delivery date to the site, inventory at the site, use by each patient, and amount returned to Millennium (or disposal of the drug, if approved by Millennium) will be maintained by the clinical site. These records will adequately document that the patients were provided the doses as specified in the protocol and should reconcile all study drug received from Millennium. Accountability records will include dates, quantities, batch/serial numbers, expiration dates (if applicable), and patient numbers. All unused, unopened, or expired MLN8237 can be returned to Millennium or destroyed per local institutional policy upon confirmation that the last patient

enrolled into the study has completed the treatment period. If a site is unable to destroy their remaining supply of study drug, they may use the "Return Drug for Destruction Form" found in the N2009-03 study specific page of the NANT Website. If a site possesses drug destruction capabilities then all study drug is to be destroyed by the site according to the site's drug destruction policy. The site will maintain detailed records of the drug reconciliation and destruction with the study files. Documentation of the site's drug destruction policy may be requested by Millennium Pharmaceuticals (or designee) at any time during the course of this study. All material containing study drug will be treated as hazardous waste in accordance with governing regulations.

